8.4 Handling of Missing Data

Missing data will be handled as follows:

Table 3. Handling of Missing Data

Data	Handling Convention
Adverse event onset date	
If onset date is completely missing, impute with the date of first dose.
 
If year is missing, impute with the year of enrollment.
 
If only year or if year and day are present:
 
 • If year = year of first dose, then set month and day to the date of the first dose. • If year < year of first dose, then set month and day to December 31. • If year > year of first dose, then set month and day to January 1. 
If month and year are present, but day is missing:
 
 • If year = year of first dose and 
 ○ If month = month of first dose, then set day to day of first dose. ○ If month < month of first dose, then set day to the last day of the month. ○ If month > month of first dose, then set day to the first day of the month. • If year < year of first dose, then set day to the last day of the month. • If year > year of first dose, then set day to the first day of the month. • For all other cases, set onset date to the date of first dose.
Adverse event end date	
If the end date is partially or completely missing, set to the last date the subject was known to be in the study.

Concomitant medications start date	
If start date is completely missing, it will not be imputed.
 
If only year or if year and day are present, set the month and day to January 1.
 
If year and month are present and day is missing, set day to the first day of the month.

Concomitant medications end date	
If end date is missing, frequency is “1X” and the medication is not listed as “ONGOING”, then end date should be set to equal the start date.
 
If the criteria above are not met, the following imputation rules apply:
 
 • If end date is completely missing, it will not be imputed. • If only year or if year and day are present, set the month and day to December 31. • If year and month are present and day is missing, set day to the last day of the month.
Concomitant medications time of dosing	
If time of dosing is missing for symptom relief medication, it will be imputed as the time of the FLU-PRO Questionnaire completion for that date.
 
If there is no FLU-PRO Questionnaire completed on that date, the time will be imputed as 12:00 p.m.

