A central laboratory will be used for laboratory safety tests, anti-influenza antibodies and virology testing. Laboratory safety tests will include hemoglobin, hematocrit, complete blood count (total and differential), platelet count, random blood sugar, total cholesterol, HDL, LDL, triglycerides, albumin, AST, ALT, GGT, alkaline phosphatase, bilirubin (total/direct), BUN, creatinine, sodium, potassium, chloride and routine urinalysis (glucose, protein and blood). Virology testing will include RT-PCR assay ePlex[®] Respiratory Pathogen Panel (GenMark, Carlsbad, CA) to identify influenza A (non-specific as to subtype); influenza A H1, H1N1 (2009) and H3 subtypes; influenza B; respiratory syncytial virus A and B (RSV); parainfluenza 1, 2, 3 and 4; human metapneumovirus (hMPV); adenovirus (A-F); human rhinovirus/enterovirus; coronavirus NL63, HKU1, 229E and OC43; *Chlamydomphila pneumoniae*; and *Mycoplasma pneumoniae* (baseline and day 7 nasopharyngeal swabs), culture (baseline and day 7 nasopharyngeal swabs), and quantitation of influenza viruses by TCID₅₀ (baseline and days 2, 3 and 7 nasopharyngeal swabs). Follow-up samples (days 2, 3, 7 and 22) collected from subjects who do not test positive for influenza A or influenza B at baseline will not be analyzed for quantitative influenza viral titer.

This study is expected to run from December 2017 through April 2019.

Rationale for important issues in the study design is described below:

- *Choice of NTZ dose and duration of treatment.* The dose of NTZ used for this clinical trial (600 mg b.i.d. for 5 days) was selected based upon results of a Phase 2b/3 dose-range finding clinical trial (Study RM08-3001) conducted in the United States during the 2010-2011 flu season. In that study, treatment with 600 mg NTZ b.i.d. for 5 days was associated with a statistically significant reduction in time from first dose to alleviation of symptoms compared to the placebo. A 300 mg NTZ dose group also experienced a reduction of time to alleviation of symptoms compared to the placebo, but the difference was not statistically significant. The 600 mg NTZ dose was well tolerated. Adverse events reported for subjects receiving the

600 mg dose were similar to those of subjects receiving the placebo, with the exception of a higher rate of diarrhea (8.1% compared to 3.3% for the placebo).

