5.2 Baseline (day 1, same day as screening evaluation)

At baseline, the following procedures will be carried out:

- 1) Collection of two nasopharyngeal swabs (one from each nostril) using nylon flocked dry swabs (Copan Diagnostics) for RT-PCR and culture;

- 2) Collection of blood sample for anti-influenza antibodies;
- 3) Collection of blood sample for laboratory safety tests including hemoglobin, hematocrit, complete blood count (total and differential), platelet count, random blood sugar, total cholesterol, HDL, LDL, triglycerides, albumin, AST, ALT, GGT, alkaline phosphatase, bilirubin (total/direct), BUN, creatinine, sodium, potassium, chloride;
- 4) Collection of a urine sample for routine urinalysis (glucose, protein and blood);
- 5) Review and recording of any concomitant medications;
- 6) Provision of an electronic diary to subject via his/her own smartphone or a provisioned device, and subject completion of baseline electronic diary under supervision and instruction of study site personnel;
- 7) Randomization and dispensing of study medication (medication assigned in sequential order);
- 8) Administration of the first dose of study medication with food (< 1 hour after food intake) under observation of Investigator or a member of Investigator's staff, and entry in diary; and
- 9) Instruct subject regarding:
 - a. *Administration of study medication.* Subjects will be instructed to take the study medication (two tablets) twice daily with food (< 1 hour after food intake). The patient should take his/her second dose as close as possible to 12 hours after the first dose. Then he/she will take the study medication every 12 hours for the remaining 4 days.
 - b. *Concomitant medications.* Subjects will be instructed that they may take acetaminophen for fever if their oral temperature is $\geq 100.4^{\circ}\text{F}$ (38°C). No other symptom relief medication should be used.
 - c. *Completion of patient diary.* Subjects will be instructed on completion of the electronic diary.
 - d. *Use of birth control.* Female subjects of childbearing potential, if sexually active, will be instructed to continue an acceptable method of birth control for the duration of the study and for 1 month post-treatment. Acceptable methods of birth control include a double barrier method, oral birth control pills, an IUD, or medroxyprogesterone acetate administered intramuscularly.

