11.1.1 Summary of All Treatment Emergent Adverse Events (TEAEs)

The summary of all TEAEs will summarize the following:

- The total number of TEAEs;
- The number and percentage of subjects with at least one TEAE;
- The number and percentage of subjects with at least one SAE;
- The number and percentage of subjects with a TEAE by the maximum severity grade; and
- The number and percentage of subjects with a TEAE by the closest relationship to the study drug.

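### SAP Table 3 gives an adverse event with no recorded year the enrollment year, so a January event in a December enrollee is dated about 10 to 12 months before first dose

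*SAP*

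**What the plan says.** SAP section 8.4, Table 3, gives these rules for an incomplete adverse-event onset date:

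- Year missing: "If year is missing, impute with the year of enrollment".
- Month known, day missing, year equal to the first-dose year, earlier month: "If month < month of first dose, then set day to the last day of the month".
- Month missing: "If year = year of first dose, then set month and day to the date of the first dose".
- Whole date missing: "If onset date is completely missing, impute with the date of first dose".
- A last bullet, listed under the missing-day branch: "For all other cases, set onset date to the date of first dose".

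On timing, Protocol section 3 states: "This study is expected to run from December 2017 through April 2019". The heading of Protocol section 5.2 begins "Baseline (day 1, same day as screening evaluation", and that section includes randomization and the observed first dose. The year of enrollment is therefore the year of first dose. Section 5.7 puts the last visit at day 22, with up to 3 further days allowed.

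Protocol section 10 limits adverse events to changes that arise once the first dose has been taken. The safety summaries in SAP section 11.1.1 count treatment-emergent events, for example "The number and percentage of subjects with at least one TEAE". Neither document says how an event is classed as treatment-emergent.

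**The concern.** The missing-year rule works only when onset and first dose fall in the same calendar year. The trial recruits in influenza seasons that straddle 1 January and follows each subject for about three weeks. A January onset in a December enrollee therefore belongs to the next calendar year, and the rule assigns it to the wrong one.

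The result also runs against the rest of Table 3. A subject with no onset date at all is given the date of first dose, which is plausible. A subject for whom 5 January was recorded is given a date that the protocol's own definition rules out. More information produces a worse date.

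At stake are the onset dates in the adverse-event listing (SAP section 11.2) and, depending on how the flag is built, the treatment-emergent counts in sections 11.1.1 and 11.1.2.

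**Working it through.** The plan states no figure to reproduce. The check applies the Table 3 rules literally.

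**Inputs**
- Imputed year = enrollment year = first-dose year (SAP 8.4; Protocol 5.2).
- Follow-up ends 21 days after day 1, or 24 days with the visit window (Protocol 5.7).
- A true adverse-event onset is not before first dose (Protocol 10).

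**Which first doses are exposed.** A January onset is possible if first dose plus follow-up reaches 1 January. 11 December + 21 days = 1 January; 8 December + 24 days = 1 January. Exposure therefore runs from 8 or 11 December to 31 December.

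**Month and day recorded, year missing.** If the true onset is *t* days after first dose and falls in the next year, the imputed onset is 365 − *t* days before first dose. (Neither year-end involves a 29 February.)
- *t* = 1: 365 − 1 = 364 days before.
- *t* = 24: 365 − 24 = 341 days before.
- First dose 28 December 2018 (day 362 of the year), onset 5 January: imputed 5 January 2018, and 362 − 5 = 357 days before.

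**Month recorded, day and year missing.** January is earlier than December, so the imputed date is 31 January of the first-dose year. The gap is the first dose's day of the year minus 31.
- 8 December: 342 − 31 = 311 days before.
- 31 December: 365 − 31 = 334 days before.
- 28 December: 362 − 31 = 331 days before.

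The full range is 311 to 364 days. At 30.4375 days per month, that is 10.2 to 12.0 months.

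**Cases that come out right.** If the month is missing too, or the whole date is missing, onset becomes the date of first dose (gap 0). As a control, take every 2018 first-dose date with every onset 0 to 24 days later in the same calendar year. That is 341 × 25 + (24 + 23 + … + 1) = 8,525 + 300 = 8,825 pairs. None is imputed before first dose, with the day known or missing. The fault is confined to the year boundary.

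**Knock-on for duration.** Table 3 sets a missing end date to the last date the subject was known to be in the study. In the 28 December 2018 example with a last date of day 22 (18 January 2019), an onset of 5 January 2018 implies a duration of 365 + 13 = 378 days.

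**The case against.** **The event need not be lost.** A reader might infer that these events drop out of the treatment-emergent tables. The documents do not support that. The SAP expands the abbreviation and uses it, but gives no rule comparing onset with first dose. Since the protocol already restricts adverse events to those after first dose, the programmer could count every reported event as treatment-emergent. The event would then stay in the tables and only its listed date would be wrong. This objection stands: loss from the tables is conditional.

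**The trigger is rare.** Adverse experiences go into an electronic diary daily (Protocol 5.10), sites review entries daily (5.3), and the data system applies real-time checks and queries (7.1). A date nearly a year before dosing would also be conspicuous in the listing. This stands as to frequency, but it does not make the rule correct.

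**The catch-all bullet may cover it.** It does not clearly do so. It sits under the missing-day branch, and January with no day has already been assigned by the earlier-month line. A known month and day is completed by the missing-year line and never reaches that branch.

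**A percentage is tempting.** One could count the share of winter enrollment dates whose follow-up crosses 1 January. The documents give no enrollment calendar from which to do this. The protocol's revision history labels version 1.2, effective 28 December 2017, a pre-enrollment update. On that record the first year-end offers at most four exposed dates (28 to 31 December). A share of dates is also not a share of subjects or events.

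**Conclusion.** The point holds and is minor. As written, Table 3 misdates every adverse event that has a January month, no year, and a first dose in the preceding December. The error is 311 to 364 days before dosing, and the date contradicts the protocol's definition of an adverse event.

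The wrong listed date follows from the documents alone. An effect on the treatment-emergent counts rests on one further assumption: that the flag compares imputed onset with first dose. That is usual, but the SAP does not say it.

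The number of events is probably very small, because the month must be recorded and the year not. The exposure lies mainly at the December 2018 year-end. No percentage can be supported.

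**What to change.** In SAP Table 3, keep "If year is missing, impute with the year of enrollment" and add: *unless that places the onset before first dose and the following calendar year places it within the subject's follow-up, in which case use the following year*. Then apply the existing missing-day rules.

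For first dose 28 December 2018, 5 January becomes 5 January 2019 (8 days after dosing). January with no day becomes 1 January 2019 (4 days after) under the existing later-year rule. An entry of 15 November with no year stays at 15 November 2018, because November 2019 lies outside follow-up. A blanket fallback to first dose would instead overwrite that recorded month and day, so it should not be used.

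In SAP section 11.1, add a sentence stating how imputed onset determines treatment-emergent status.

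The cost is one clause and one sentence, with a small programming change. No new data are needed and the efficacy analyses are untouched. SAP section 6 requires the plan to be final before database lock, so the change should be made before then.

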9. GENERAL CHARACTERISTICS

9.1 General Characteristics Tables and Figures

All tables will present data for the overall study and by treatment group.

9.1.1 Disposition of Subjects

The disposition tables will summarize the count and percentage of subjects who completed or discontinued from the study and the mean (SD), median (IQR), and minimum and maximum number of days in the study.

Analysis Population(s):	All Treated Confirmed Influenza
Derived Variables:	Number of days in study = date of study completion/early termination – date of randomization + 1

9.1.2 Protocol Deviations

The deviations tables will summarize the count and percentage of subjects with protocol deviations by deviation classification (major, minor, or GCP) and the common deviation term.

Analysis Population(s):	All Treated Confirmed Influenza
Derived Variables:	None

9.1.3 Demographics

The demographics tables will summarize sex, age at screening (years), race, height (cm), weight (kg), BMI (kg/m²), smoking status and vaccination status as collected at screening/baseline using descriptive statistics.

Analysis Population(s):	All Treated Confirmed Influenza
Derived Variables:	
 • Age in years at screening = date of screening – date of birth • BMI = weight in kg / (height in cm / 100)²

9.1.4 Disease Characteristics

The disease characteristics tables will summarize oral temperature in-office (°F), oral temperature (°F), time from onset of symptoms to the time of first dose (hours), virus infection(s), respiratory symptoms, and constitutional symptoms as collected at screening/baseline using descriptive statistics.

Analysis Population(s):	All Treated Confirmed Influenza
Derived Variables:	Oral temperature = maximum of oral temperature recorded in the clinic at screening/baseline and self-report by the subject

9.1.5 Prior and Concomitant Medication

The prior and concomitant medication tables will summarize the number and percentage of subjects receiving each medication by Level 4 Anatomical Therapeutic Chemical (ATC) classification and standardized medical name.

Analysis Population(s):	All Treated Confirmed Influenza
Derived Variables:	
 • Prior medication classification = medications with stop dates prior to screening date • Concomitant medication classification = medications with administration occurring on or after the date of the first administration of study drug until the end of the study

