4.1 Inclusion Criteria

- 1) Male and female subjects at least 12 years of age
- 2) Presence of clinical signs and/or symptoms consistent with an acute illness compatible with influenza infection (each of the following is required):
 - a) oral temperature of $\geq 99.4^{\circ}\text{F}$ or $\geq 37.4^{\circ}\text{C}$ (obtained in office or self-measured within 12 hours prior to screening – if self-measured, subject must also have taken an antipyretic within 4 hours prior to screening), AND
 - b) at least one of the following respiratory symptoms (cough, sore throat, nasal obstruction), AND
 - c) at least one of the following constitutional symptoms (fatigue, headache, myalgia, feverishness).
- 3) Confirmation of influenza A or B infection in the local community by one of the following means: (a) the institution's local laboratory, (b) the local public health system, (c) the national public health system, or (d) a laboratory of a recognized national or multinational influenza surveillance scheme

- 4) Onset of illness no more than 40 hours before enrollment in the trial
Note: Time of onset of illness is defined as the earlier of:
 - a) the time when the temperature was first measured as elevated, OR
 - b) the time when the subject experienced the presence of at least one respiratory symptom AND the presence of at least one constitutional symptom.
- 5) Willing and able to provide written informed consent (including assent by legal guardian if under 18 years of age) and comply with the requirements of the protocol, including completion of the patient diary

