5.10 Electronic Subject Diary

Electronic subject diaries will be completed twice daily through day 21. The electronic diaries will capture the following information:

- 1) Medication intake (twice daily at time of medication intake).
- 2) Oral temperature (twice daily at time of medication intake). Use standard electronic oral thermometer provided by Sponsor. Oral temperature should, preferably, be recorded prior to acetaminophen dosing or greater than 4 hours after acetaminophen dose.
- 3) Use of other medications taken (including acetaminophen) by the subject not previously captured in the subject's medication history. Document in detail including dose in milligrams or other applicable units, time of ingestion, and the reason for use of the medication (at time of medication intake).
- 4) FLU-PRO Questionnaire (once daily between 7 pm and 11 pm) to characterize symptoms of influenza.
- 5) Activity assessment using an 11-point visual analog scale (0= unable to perform normal activity, 10= fully able to perform normal activity) (once daily between 7 pm and 11 pm).
- 6) Adverse experiences (once daily between 7 pm and 11 pm).

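### SAP 9.1.5 separates prior from concomitant medication by calendar date, so an antipyretic taken on day 1 before the first dose is tabulated as concomitant

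*SAP*

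**What the plan says.** SAP 9.1.5 has two rules. Prior medications are "medications with stop dates prior to screening date". Concomitant medications are "medications with administration occurring on or after the date of the first administration of study drug until the end of the study". Both are tied to dates, with no clock time. The section tabulates subjects by ATC level 4 class and medication name. The displays are Tables 14.1.5.1 and 14.1.5.2 (prior) and 14.1.6.1 and 14.1.6.2 (concomitant).

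The protocol puts the relevant steps on one day. The heading of Protocol 5.2 includes "Baseline (day 1, same day as screening evaluation". Step 5 of that visit is "Review and recording of any concomitant medications", step 6 provides the diary, step 7 is randomization, and step 8 is "Administration of the first dose of study medication with food" under observation. Criterion 2a in Protocol 4.1 adds a condition on the temperature requirement: "if self-measured, subject must also have taken an antipyretic within 4 hours prior to screening".

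Nothing elsewhere separates pre-dose from post-dose use on day 1:

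- The medication listings in SAP 9.2 (Table 4) carry start and stop dates only.
- SAP 8.4 (Table 3) sets a missing end date of a one-off, non-ongoing medication to its start date, which leaves it on day 1.
- The diary in Protocol 5.10 does record "time of ingestion, and the reason for use of the medication", but only for medications not already in the subject's history.

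SAP 10.6.2 uses any concomitant medication (yes/no) as a factor in the exploratory pharmacokinetic analysis of NTZ-treated subjects.

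**The concern.** A dose taken before randomization cannot be a consequence of treatment, yet the date rule puts it in the class meant to describe use on study. One of the two routes through criterion 2a produces such doses by design, so this is not a rare edge case.

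On-study antipyretic use matters for interpretation. Protocol 9.6 disallows analgesics and antipyretics during the study, apart from acetaminophen for an oral temperature of at least 100.4°F (38°C). The concomitant medication tables are where a reader would check whether the arms differed. Adding pre-dose use, which randomization should make similar in both arms, raises both percentages and pulls them together. In SAP 10.6.2, a subject whose only medication was the pre-dose antipyretic is coded as a concomitant medication user.

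**Working it through.** The documents give no figure on this point to reproduce. The check is of the rule itself, and then of how it carries over to subject counts.

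**Step 1. The rule applied to one dose.** Let S be the screening date, F the date of first dose and E the stop date. Prior requires E < S. Concomitant requires intake on or after F. Protocol 5.2 gives S = F. A single antipyretic dose taken earlier that day has E = S = F, so it fails the prior rule and meets the concomitant rule. The only exception is a 4-hour window that crosses midnight, which needs screening before 04:00.

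I enumerated single doses taken 5 to 240 minutes before screening, in 5-minute steps, with the first dose assumed 60 minutes after screening on the same date:

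| Screening hours (assumed) | SAP rule: prior | SAP rule: concomitant | Date-time rule: prior |
|---|---|---|---|
| 08:00–18:00 | 0% | 100% | 100% |
| 04:00–24:00 | 0% | 100% | 100% |
| Any hour | 8.9% | 91.1% | 100% |

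**Step 2. From doses to subjects.** Let q be the proportion taking the drug on day 1 before first dose, the same in both arms by randomization. Let w and v be the proportions using it after first dose among subjects with and without that pre-dose use.

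- True on-study use: u = q·w + (1 − q)·v
- Use as tabulated: q + (1 − q)·v
- Overstatement: q·(1 − w), the fraction with pre-dose use only
- True difference between arms: q·Δw + (1 − q)·Δv
- Tabulated difference: (1 − q)·Δv

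The table therefore loses whatever difference exists among subjects who took a pre-dose antipyretic. The difference is diluted whenever that lost part points the same way as the rest.

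**Step 3. Illustration.** Assume true use of 30% versus 40%, q of 30% or 60%, and later use independent of pre-dose use (w = v = u). Tabulated use is then 1 − (1 − u)(1 − q).

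| q | First arm | Second arm | Difference (true: 10 points) |
|---|---|---|---|
| 30% | 1 − 0.70 × 0.70 = 51% | 1 − 0.60 × 0.70 = 58% | 7 points |
| 60% | 1 − 0.70 × 0.40 = 72% | 1 − 0.60 × 0.40 = 76% | 4 points |

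**Step 4. If independence fails.** Take the opposite extreme, where on-study users come first from the pre-dose users. Tabulated use is then the larger of q and u. At q = 30% the table shows 30% versus 40%: no error. At q = 60% it shows 60% versus 60%: a smaller overstatement than 72% versus 76%, but no difference left. Positive association reduces the overstatement without necessarily protecting the difference.

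**The case against.** The strongest reply is that this affects very little, and much of that reply stands. The tables are descriptive, no test is planned on them, and the rule is explicit, reproducible and identical in both arms. It can also be said that a dose taken within 4 hours of screening may still be acting at the first study dose; Protocol 5.10 itself prefers temperatures taken more than 4 hours after acetaminophen. That concerns overlap of effect. It does not make a pre-dose intake a measure of use on study.

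Several stronger readings are tempting and should not be drawn:

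- **That the primary result is affected.** SAP 10.2 and 10.4.1 place symptom relief medication by date and time of intake against 24-hour diary periods. The list of those medications is selected from the concomitant medication listing, but once selected an intake acts through its clock time, not through its label in a table.
- **That every subject entering on a self-measured temperature is miscounted.** The 100% in Step 1 refers to doses. The tables count subjects, and one who takes the same drug again after dosing is correctly a concomitant user.
- **That a difference between arms would be hidden.** In the independence illustration it shrinks to 7 or 4 points. It vanishes only in an assumed extreme that nothing in the documents supports.
- **That pre-dose use would become a protocol deviation.** Protocol 9.5 makes disallowed medication a major violation, and SAP 8.1 removes some major deviations from the Per Protocol population. However, Protocol 7.2 has the investigator document deviations, with review by the clinical research associate. No text derives them from the SAP 9.1.5 class.
- **That clock times already exist for these doses.** The antipyretic would ordinarily be recorded at step 5 of the baseline visit, before the diary is provided at step 6, so its time may be missing. This objection stands and shapes the fix.

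**Conclusion.** The point holds as a minor one. For screening at or after 04:00, the SAP 9.1.5 rule classes every single-dose pre-screening antipyretic taken on day 1 as concomitant and none as prior. The subjects wrongly counted as concomitant users are those with pre-dose use and no later use of the same drug. They inflate Tables 14.1.6.1 and 14.1.6.2. They are absent from Tables 14.1.5.1 and 14.1.5.2, unless a separate record of the drug stopped on an earlier date. If they took nothing else, they are also miscoded in the SAP 10.6.2 factor.

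The size depends on the fraction with pre-dose use only, which the documents do not give; the percentages in Steps 3 and 4 show direction and range under stated assumptions. The conclusion assumes that screening and first dose share a date, as Protocol 5.2 states, and that the medication is recorded as stopped on day 1. The primary and key secondary tests, alpha and power do not change.

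**What to change.** In SAP 9.1.5, define prior as last taken before the date and time of first dose, and concomitant as any intake at or after it. The first-dose date and time are already analysis variables in SAP 10.2.

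For day-1 records without a clock time:

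- Class as prior any medication recorded at the baseline review (Protocol 5.2, step 5, which precedes the first dose at step 8) as already taken and not ongoing.
- Show any remaining record as 'Day 1, timing unknown'.

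State that the rule governs only the prior and concomitant tables and the SAP 10.6.2 factor. The Table 3 imputation of missing dosing times for symptom relief medication then stays as it is for the endpoint derivations. Say also that the pool of records from which symptom relief medications are selected does not change; otherwise moving pre-dose records to the prior class could remove them from that pool.

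The cost is one SAP clarification before database lock and unblinding, a small amount of programming, and possibly a small 'timing unknown' row. SAP version 1.2 already makes a similar clarification for missing concomitant medication dates and times. No new data collection is needed.
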